11 STUDY PROCEDURES AND GUIDELINES

Prior to conducting any study-related activities, written informed consent and the Health Insurance Portability and Accountability Act (HIPAA) authorization must be signed and dated by the subject. If appropriate, assent must also be obtained prior to conducting any study-related activities. Study visits will be conducted on the scheduled day or within +/- 2 days for weekly study visits and +/- 7 days for monthly visits.

11.1 Schedule of Events

11.1.1 Main Study Phase

TABLE 4	SCREEN		RUN-IN PHASE		DOSE ESCALATE				TREATMENT PHASE							
					M2	M2	M 2		M 3	M 5	M 7	M 9	M 11	M 12	M 13	
MONTH*	M1		M1		W5	W6	W8	W9	W11	W17	W25	W33	W41	W45	W53	
WEEK	W 1	W2	W3	W 4												
VISIT NUMBER	0		1		2	3	4	5	6	TF1	7	TF2	TF3	TF4	8	
Screening Labs (Renal function panel, Lipid panel, HbA1C, Urine sample Alb/Creat)	X															
Safety Labs (Renal function panel) Mag level*					X*	X	X	Optional	X*		X					X*
History & Targeted Assessment			X								X					X
EKG			X													
Vital Signs or 24-hour BP SphygoCor cuff * (includes central aortic BP))	X		X		X*		X		X*		X					X
Phone Call										X		X	X	X		
MRI					X				X							X
Research Labs/Monocyte Studies, (including PIP, PIINP, CITP and chemokines CCL2, CX3, CL1, and CCL5)					X				X							X
Insulin/Glucose (HOMA-IR)					X											X
HbA1C					X						X					X
Plasma Renin/Aldosterone					X											X
Medication Log		X				X			X	X	X	X	X	X	X	X
Pill counts					X				X		X					X
Dietary survey/instructions		X														X
Urine sample (Albumin/Creat)		X			X				X		X					X
Spot Urine Na/K/Creat					X											
Interim Event log					X		X		X	X	X	X	X	X	X	X
Questionnaire & Instructions			X													

A complete medical history and physical exam will be performed at baseline and will include a 12-lead electrocardiogram (EKG), cardiovascular risk factor assessment, intercurrent CV events, 7-day physical activity recall, active/passive smoking questionnaires and dietary recall questionnaire. Sitting systolic blood pressure, pulse rate, body weight, interim event logs, pill counts, medication logs will be recorded at most clinic visits. Central aortic blood pressure and pulse wave velocity will be obtained during

visit 2 (base), 6 (mid-point) and 8 (exit) while 24-hour BP will be measured at Visit 2 and 6.

Dietary Na⁺ consumption: Since Na intake is an important determinant of MR responsiveness we will ensure that all patients receive dietary survey/instructions (Visit 0) on maintaining a personalized diabetic diet that is stable and is medium to low in sodium (<4 g). We will obtain Na, K and Creatinine levels (Visit 1) to assess Na intake. The kawasaki formula will be used to estimate 24 hour urine.

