or switch to placebo. The median increase in serum potassium levels after 8 weeks, the primary endpoint, was significantly greater in patients switched to placebo than in those who continued taking the active drug (0.72 vs 0.00 mEq/L). Patients who continued receiving patiromer were less likely to experience recurrent hyperkalemia than those switched to placebo (15% vs 60%) and more likely to remain on a RAAS inhibitor (94% vs 44%).(17) In another study in 25 patients with hyperkalemia and chronic kidney disease, patiromer 8.4 g twice daily significantly decreased serum potassium levels as early as 7 hours after administration of the first dose (-0.21 mEq/L). After 48 hours, mean levels had dropped by 0.75 mEq/L.(18) The Phase 3 studies confirm that the 16.8 g per day dose is reasonable in patients with mild hyperkalemia (defined as potassium concentration >5.0 to 5.5 mEq/L at baseline or at any time during dose titration) while a starting dose of 16.8 g/d is reasonable in patients with moderate hyperkalemia [potassium concentration >5.5 to <6.0 mEq/L]. The mean reduction in K⁺ with doses in AMETHYST-DN with this dose was 0.51 (95% CI, 0.38-0.64) mEq/L in the mild hyperkalemia group and 0.87 (95% CI, 0.60-1.14) mEq/L in the moderate hyperkalemia group.

Risk of Hypokalemia/Hypomagnesemia with Patiromer: In the PEARL-HF trial, the incidence of hypokalemia was 5% in the 30 g/d fixed dose group compared to 0% of the placebo group (titration of Patiromer was not allowed). The incidence of hypomagnesemia was 24% and 2% in the placebo group. In an open-label of Patiromer (RLY5016-204 trial), the starting dose of RLY5016 was 20 g/d and was titrated at weekly visits according to potassium level. With careful titration and follow-up, only one of 63 patients developed hypokalemia (serum K+<3.5), which was promptly reversed by decreasing the dose of Patiromer. Hypomagnesemia (serum Mg2+< 1.8 mg/dL) occurred in 8/63 (13%) of patients. In AMETHYST-DN, over the 52 week duration of the trial, hypomagnesemia (7.2%) was the most common treatment-related adverse event, with hypokalemia (<3.5 mEq/L) occurring in 5.6% of patients.

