9 STUDY TREATMENTS

9.1 Method of Assigning Subjects to Treatment Groups

Up to 50 eligible patients will participate in the study. All study participants will undergo a two week run-in period with Patiromer. Then study medication will be commenced at 12.5 mg Spironolactone and Patiromer 8.4 g/d and escalate to 25 mg Spironolactone over

4 weeks. If needed, to manage K⁺, Patiromer will increase to 16.8 g/d. Then the treatment phase will commence with tolerated dose of Spironolactone along with Patiromer for 48 weeks.

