11.3 Urgent Study Alerts

An Investigator should be notified immediately if any of the following are noted at study visits:

Blood Pressure Immediate Alert Values:

- Systolic Blood Pressure < 80
- Systolic Blood Pressure > 180
- Diastolic Blood Pressure > 110

Acute Distress: (signs or symptoms constituting an emergency):

- Chest Pain
- Severe Respiratory Distress
- Acute Neurological Symptoms

Urgent Lab Values:

- Potassium \leq 3.0 mEq/L
- Potassium \geq 6.0 mEq/L
- Glucose < 50 mg/dL

- Glucose >350 mg/dL
- Creatinine doubling from last value

Coronavirus Outbreak (COVID-19) Management Plan under Public Health Mandates

The following guidelines were developed under policies set forth by UH Cleveland Medical Center, the University of Maryland, NYU Winthrop, and MetroHealth Systems.

Recruitment and Enrollment

The new public health mandates concerning the COVID-19 have led to the decision to permanently close enrollment. At the time COVID-19 policies were implemented, University of Maryland, NYU Winthrop, and MetroHealth Systems had not enrolled any patients. Study procedures for the remaining UH participants will revert to the original procedures described in Section 11 “Procedures and Guidelines” once the mandates are lifted.

Active Participants and Follow up Visits

At University Hospitals, all active participants fell into the “treatment phase” of the study procedures timeline of events (See 11.1.2 Main Study Phase).

TREATMENT-PHASE

In order to simultaneously reduce transmission of the virus while maintaining the management of participant’s follow up care to the best extent possible, pertinent study activities (i.e. safety labs & vital signs) will be attempted in conjunction with any provider scheduled clinical encounter deemed essential for clinical care. If this is not possible, patients will be given an additional prescription until the essential study activities can be performed safely (length of prescription may vary based on patients’ recent bloodwork and BP/HR, policies, and investigator’s medical judgment).

Additional important details

Remote study visits are not appropriate for this study.

Participants will be compensated for their participation at the same amount specified in the original consent.

All enrolled participants will be notified by phone call of these protocol changes enacted during the period of public health mandates.

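### Magnesium is apparently not measured between Week 11 and Week 53 and has no alert value, although the protocol's own background ranks hypomagnesemia first among patiromer's treatment-related events

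*Combined protocol and SAP*

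**What the plan says.** **Risk.** Section 2.1, in its paragraph on hypokalemia and hypomagnesemia, gives three figures for patiromer:
- 52-week trial in diabetic kidney disease: "hypomagnesemia (7.2%) was the most common treatment-related adverse event, with hypokalemia (<3.5 mEq/L) occurring in 5.6% of patients".
- Open-label study with weekly titration: "Hypomagnesemia (serum Mg2+< 1.8 mg/dL) occurred in 8/63 (13%) of patients".
- Trial with a fixed 30 g/d dose and no titration: "The incidence of hypomagnesemia was 24% and 2% in the placebo group".

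Section 3.1.1.1 lists hypomagnesemia among the common side effects.

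**Schedule.** In Table 4 (section 11.1.1) the Visit 0 panel is "Screening Labs (Renal function panel, Lipid panel, HbA1C, Urine sample Alb/Creat". Magnesium appears only in the row labelled "Safety Labs (Renal function panel) Mag level", where the label ends in an asterisk. That row has a starred mark at Visits 2, 6 and 8 (W5, W11, W53), a plain mark at Visits 3, 4 and 7 (W6, W8, W25), and an optional draw at W9. Section 11.2 names magnesium separately from the BUN, creatinine and electrolyte safety panel.

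**Alerts.** The urgent laboratory values in section 11.3 cover high and low potassium, high and low glucose, and "Creatinine doubling from last value". Magnesium is absent.

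**Start of patiromer.** Section 9.1 says: "All study participants will undergo a two week run-in period with Patiromer". Section 9.3.3 gives a patiromer run-in only when screening potassium exceeds 5.5. It starts both drugs together, without a run-in, at 5.3-5.5, and uses a spironolactone run-in at 4.6-5.2.

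**Status.** The COVID-19 plan placed under section 11.3 closes enrollment for good. It says that three of the sites had enrolled nobody and that every active participant was already in the treatment phase.

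**The concern.** The event that the background ranks first is the one the schedule follows least closely. Potassium is measured at every safety draw and has a low alert value. Magnesium, which was low more often than potassium in the cited 52-week trial, appears to be measured three times, with nothing planned for most of the treatment phase.

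Two things are at stake:
- **Detection.** Low magnesium without symptoms between W11 and W53 would be found only by an unscheduled test. Section 9.3.3 allows the patiromer dose to be raised according to potassium during the study, so exposure could increase within that interval with no magnesium check.
- **Interpretation.** Section 6.3 makes laboratory change and adverse-event incidence the safety evaluations, and there is no control arm (section 9.3.2). Where the first magnesium value is already on patiromer, a pre-existing low value cannot be separated from a drug effect.

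**Working it through.** The documents do not state an interval between magnesium measurements, so there is no figure of that kind to reproduce. The one rate that can be checked agrees: 8/63 = 12.7%, which the protocol rounds to 13%. The 7.2% has no denominator.

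**1. Which visits carry magnesium.** The footnote to the asterisk is not in the text available to me, so its meaning has to be inferred. The final starred mark in the safety row sits one cell past the last week label, as do the last marks in the MRI and HbA1C rows, so I read it as Visit 8. Evidence that the star marks the magnesium visits:
- The row label carries an asterisk after the magnesium item, and the cells differ between plain and starred marks.
- The blood-pressure row has starred marks at Visits 2 and 6 only, and the text below the table puts 24-hour BP at exactly those visits.
- Section 11.2 keeps magnesium apart from the routine panel.

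**2. Length of the gap.**

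| Reading | Magnesium at | Intervals (weeks) | Longest |
|---|---|---|---|
| Starred visits only | W5, W11, W53 | 6, 42 | 53 - 11 = 42 |
| Every required safety draw | W5, W6, W8, W11, W25, W53 | 1, 2, 3, 14, 28 | 53 - 25 = 28 |
| Starred visits plus Visit 7 | W5, W11, W25, W53 | 6, 14, 28 | 53 - 25 = 28 |

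With the 7-day window for monthly visits (section 11) at each end, 42 weeks becomes 40 to 44. Between W11 and W53 the only other planned contacts are Visit 7 and phone calls at W17, W33, W41 and W45. The COVID-19 plan lets study safety labs wait while prescriptions are extended, so the actual interval could be longer.

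**3. Whether potassium monitoring stands in for magnesium.** In the titrated study, potassium was followed weekly; 1 of 63 patients became hypokalemic and 8 of 63 hypomagnesemic. In the 52-week trial the rates were 5.6% and 7.2%. Acceptable potassium therefore does not imply acceptable magnesium.

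**4. Who lacks a pre-binder value.** The first scheduled magnesium is at Visit 2, after the run-in.
- Under 9.1, every patient has had two weeks of patiromer by then.
- Under 9.3.3, this holds for screening potassium above 5.5. At 5.3-5.5 there is no run-in. At 4.6-5.2 patiromer is added at the one-week recheck, and the text does not place Visit 2 before or after that first dose.

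The two sections contradict each other and must be reconciled.

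**5. Expected cases.** Expected cases = N × rate. At N = 50, the planned maximum:
- 50 × 0.072 = 3.6
- 50 × 8/63 = 6.3

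The number enrolled is not given. Per 10 patients enrolled, the same rates give 10 × 0.072 = 0.72 and 10 × 8/63 = 1.27.

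**The case against.** **The asterisk is ambiguous.** This objection stands in part. The blood-pressure parallel is imperfect: the starred label includes central aortic BP, which the text requires at Visits 2, 6 and 8, yet Visit 8 has a plain mark. The month row also has an asterisk but no starred cells. If magnesium accompanies every safety draw, the longest gap is already 28 weeks. The starred-visit reading is still the more natural one, and the ambiguity itself needs a sentence in the table. The missing screening value and alert line do not depend on it.

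**A low value would not go unnoticed.** This stands against any inference that low magnesium triggers no response at all. Section 12.1 counts abnormal laboratory findings as adverse events and grades clinically significant ones by CTCAE, adverse events are asked about at every visit, and the DSMB reviews safety every 3 months (section 14). Section 11.3 governs immediate alerts only. None of these measures schedules a magnesium test, so they act only on values that someone has already obtained.

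**The expected burden is easily overstated.** A reader might apply the 24% rate and expect 50 × 0.24 = 12 cases. The documents do not support that: the rate comes from a fixed 30 g/d arm without titration (2% on placebo), whereas section 9.1 starts at 8.4 g/d and titrates. Fifty is also only an upper limit, and enrollment has closed.

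**Monitoring frequency is a clinical choice.** True, and no hypomagnesemia rate is a named endpoint; section 5 makes serious hyperkalemia the primary safety variable. The point is therefore a mismatch between stated risk and schedule, not a bias in a planned estimate.

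**Conclusion.** The point holds as a low-cost safety improvement. On the natural reading of Table 4 there are about 42 weeks (40 to 44 with visit windows) without a scheduled magnesium value, and 28 weeks on the alternative reading. Section 11.3 has no magnesium alert on either reading.

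A reader might go further and conclude that no patient has a pre-drug value. That follows only from 9.1; 9.3.3 supports it only for screening potassium above 5.5. A reader might also conclude that the remedy is a magnesium test at Visit 0. With enrollment closed and all active participants past that stage, it would change nothing.

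The gap rests on the inferred meaning of the asterisk. The ranking of hypomagnesemia as the leading event rests on one cited trial. The 3.6 to 6.3 cases assume 50 patients and that the cited rates carry over to this population.

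**What to change.** 1. State in Table 4 what the asterisk means, and that magnesium is measured on the blood already taken at Visit 7 and at any safety-lab draw made under the COVID-19 plan, for participants still in the treatment phase. On the starred-visit reading this cuts the longest gap from 42 to 28 weeks. It cannot help anyone already past Visit 7 unless a later draw is made.
2. Add a low-magnesium line to section 11.3. The level and any action are for the sponsor's clinicians.
3. Report hypomagnesemia as on-treatment incidence, with the definition used (section 2.1 cites below 1.8 mg/dL for one study), the number of patients tested at each visit and the number enrolled. State that patients with a patiromer run-in have no scheduled pre-drug value, so treatment-emergent status cannot be established for them unless another pre-drug result exists.
4. Reconcile 9.1 with 9.3.3, and record each patient's actual start of patiromer so that the group in item 3 can be identified.

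The cost is one extra analyte on blood already drawn, an amendment to the table and the alert list, and a few more alerts. The reported event rate may rise slightly because more cases are found.

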11.1.2 Demographics

Demographic information (date of birth, gender, race) will be recorded at Screening.

11.1.3 Adverse Events

Information regarding occurrence of adverse events will be captured throughout the study.

11.2 Clinical Laboratory Measurements

Urinary Na levels, albumin, and creatinine

Serum levels of carboxyl-terminal peptide of procollagen type I (PIP), carboxyl-terminal telopeptide of collagen type I (CITP), and amino-terminal peptide of procollagen type III (PIIINP) and chemokines

Safety labs (BUN, creatinine, electrolytes), HOMA-IR, Hem A1C and Plasma Renin Aldosterone, magnesium

11.3 Urgent Study Alerts

An Investigator should be notified immediately if any of the following are noted at study visits:

Blood Pressure Immediate Alert Values:

- Systolic Blood Pressure < 80
- Systolic Blood Pressure > 180
- Diastolic Blood Pressure > 110

Acute Distress: (signs or symptoms constituting an emergency):

- Chest Pain
- Severe Respiratory Distress
- Acute Neurological Symptoms

Urgent Lab Values:

- Potassium \leq 3.0 mEq/L
- Potassium \geq 6.0 mEq/L
- Glucose < 50 mg/dL

- Glucose >350 mg/dL
- Creatinine doubling from last value

Coronavirus Outbreak (COVID-19) Management Plan under Public Health Mandates

The following guidelines were developed under policies set forth by UH Cleveland Medical Center, the University of Maryland, NYU Winthrop, and MetroHealth Systems.

Recruitment and Enrollment

The new public health mandates concerning the COVID-19 have led to the decision to permanently close enrollment. At the time COVID-19 policies were implemented, University of Maryland, NYU Winthrop, and MetroHealth Systems had not enrolled any patients. Study procedures for the remaining UH participants will revert to the original procedures described in Section 11 “Procedures and Guidelines” once the mandates are lifted.

Active Participants and Follow up Visits

At University Hospitals, all active participants fell into the “treatment phase” of the study procedures timeline of events (See 11.1.2 Main Study Phase).

TREATMENT-PHASE

In order to simultaneously reduce transmission of the virus while maintaining the management of participant’s follow up care to the best extent possible, pertinent study activities (i.e. safety labs & vital signs) will be attempted in conjunction with any provider scheduled clinical encounter deemed essential for clinical care. If this is not possible, patients will be given an additional prescription until the essential study activities can be performed safely (length of prescription may vary based on patients’ recent bloodwork and BP/HR, policies, and investigator’s medical judgment).

Additional important details

Remote study visits are not appropriate for this study.

Participants will be compensated for their participation at the same amount specified in the original consent.

All enrolled participants will be notified by phone call of these protocol changes enacted during the period of public health mandates.

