3.1.1.1 Common Side Effects

- Hyperkalemia: We anticipate that approximately 1% of patients may develop serious hyperkalemia that may warrant discontinuation. However this may be considerably higher in patients with GFR of 40-50 ml/minute who will constitute a minority of the patients in the trial.
- Increases in BUN and creatinine

- Hypomagnesemia
- Gynecomastia or breast discomfort. Gynecomastia is a well-described adverse effect of spironolactone and is related to dose and duration of treatment; we anticipate that approximately 10% of patients may develop gynecomastia that may warrant discontinuation. Generally, discontinuation of treatment results in resolution of gynecomastia.

3.1.1.2 *Other Side Effects*

- Cardiovascular: Vasculitis
- Central nervous system: Ataxia, confusion, drowsiness, headache, lethargy
- Dermatologic: Erythematous maculopapular rash, Stevens-Johnson syndrome, toxic epidermal necrolysis, urticaria
- Endocrine & metabolic: Amenorrhea
- Gastrointestinal: Abdominal cramps, diarrhea, gastritis, gastrointestinal hemorrhage, gastrointestinal ulcer, nausea, constipation, flatulence, vomiting
- Genitourinary: Impotence, irregular menses, postmenopausal bleeding
- Hematologic & oncologic: Agranulocytosis, malignant neoplasm of breast
- Hepatic: Hepatotoxicity
- Hypersensitivity: Anaphylaxis
- Immunologic: DRESS syndrome
- Renal: Increased BUN, renal failure, renal insufficiency
- Miscellaneous: Fever

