7. SUBJECT SELECTION

7.1 Study Population

Subjects with a diagnosis of Type II Diabetes who meet the inclusion and exclusion criteria will be eligible for participation in this study. Labs drawn within 3 months of the screening visit may be used to determine eligibility.

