7.3 Exclusion Criteria

1. Uncontrolled hypertension (SBP>160 and/or DBP>95 mmHg at visit 0 (screening) and SBP >145 mm Hg at visit 2).
2. GFR (MDRD) of <15 at visit 0 (screening)
3. K ⁺ <4.6 meq/L at visit 0 (screening).
4. LDL cholesterol >150 mg/dL
5. Plasma triglycerides > 400 mg/dl
6. Contraindications to MRI (metallic implants, severe claustrophobia).
7. Acute coronary syndrome, Transient ischemic attack, CVA or critical limb ischemia during the last 6 months or coronary/peripheral revascularization within the last 3 months .
8. Evidence of a secondary form of hypertension.
9. Initiation of new therapy with statins, ACEI/ARB, antioxidants, CCBs, diuretics, β blockers.
10. Type I diabetes mellitus
11. Known contraindication, including history of allergy to Spironolactone or Patiromer
12. Any surgical or medical condition which might alter pharmacokinetics of drug (e.g. renal transplant, liver failure, liver transplant)
13. Concurrent potentially life threatening arrhythmia or symptomatic arrhythmia.
14. Significant hyponatremia defined as Na <130 meq/L.
15. History of prior malignancy including leukemia and lymphoma (but not basal cell skin cancer, cured squamous cell cancer and cured prostate cancer).
16. History of any severe, life-threatening disease.
17. Any surgical or medical conditions which place the patient at higher risk derived from his/her participation into the study, or likely to prevent patient from complying with requirements.
18. History of drug abuse within the last 2 years, noncompliance and unwillingness/inability to consent.
19. Pregnant women and nursing mothers
20. Class III or IV Congestive Heart Failure
21. Primary Hyperaldosteronism

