9.3.3 Dosage

If screening K 4.6-5.2; start Spironolactone “run-in phase” 25 mg qd x 1 week; at 1 week recheck K and creatinine and add Veltassa 8.4 mg qd and continue with the treatment phase

If screening K 5.3-5.5 start Spironolactone 12.5 mg and Veltassa 8.4 mg without a run-in phase and follow the Spironolactone dose escalate phase as in current protocol followed by the treatment phase

If screening K >5.5 start Veltassa “run-in phase” 8.4 mg qd x 2 weeks and Add Spironolactone after 2 weeks 12.5 mg qd with plan to dose escalate to 25 mg qd as per current protocol

The dose may need to be adjusted during the study due to safety lab results (e.g. K⁺) or if BP <100 mmHg. The study physician will adjust dose as needed.

The active ingredient is patiomer sorbitex calcium, which consists of the active moiety, patiromer, a non-absorbed potassium-binding polymer, and a calcium-sorbitol counterion. Each gram of patiromer is equivalent to a nominal amount of 2 grams of patiromer sorbitex calcium. Therefore, patients will be dosed at 8.4g of patiromer = 16.8g of patiromer sorbitex calcium (one packet) at the start of the study, increasing to 16.8g of patiromer = 33.6g of patiromer sorbitex calcium (two packets) as needed, according to the potassium levels during the study.

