13 DISCONTINUATION OF SUBJECTS

13.1 Early Discontinuation of Study Drug

A subject may be discontinued from study treatment at any time if the subject, the investigator, or the Sponsor feels that it is not in the subject's best interest to continue. The following is a list of possible reasons for study treatment discontinuation:

Subject withdrawal of consent (or assent)

Subject is not compliant with study procedures

Adverse event that in the opinion of the investigator would be in the best interest of the subject to discontinue study treatment

Protocol violation requiring discontinuation of study treatment

Lost to follow-up

Sponsor request for early termination of study

Positive pregnancy test (females)

If a subject is withdrawn from treatment due to an adverse event, the subject will be followed and treated by the Investigator until the abnormal parameter or symptom has resolved or stabilized.

All subjects who discontinue study treatment should come in for an early discontinuation visit as soon as possible and then should be encouraged to complete all remaining scheduled visits and procedures.

All subjects are free to withdraw from participation at any time, for any reason, specified or unspecified, and without prejudice.

Reasonable attempts will be made by the investigator to provide a reason for subject withdrawals. The reason for the subject's withdrawal from the study will be specified in the subject's source documents.

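### The only creatinine alert compares each result with the one before it, so a doubling from screening spread over two or more panels triggers no immediate notice

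*Combined protocol and SAP*

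**What the plan says.** Section 11.3 (Urgent Study Alerts) requires immediate notice to an investigator for listed findings. The numeric items other than creatinine are fixed levels: systolic pressure below 80 or above 180, diastolic above 110, potassium at or below 3.0 or at or above 6.0, glucose below 50 or above 350. The creatinine item is "Creatinine doubling from last value".

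A screening value is available as a reference, because the schedule in 11.1.1 has at Visit 0 "Screening Labs (Renal function panel, Lipid panel, HbA1C, Urine sample Alb/Creat". As I read that schedule, whose columns are broken in the text, renal panels follow at Visits 2, 3, 4, 6, 7 and 8, with Visit 5 optional. For screening potassium of 4.6–5.2, section 9.3.3 adds a check during the spironolactone run-in: "at 1 week recheck K and creatinine and add Veltassa 8.4 mg qd and continue with the treatment phase". It gives no creatinine level for action.

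Section 3.1.1.1 lists "Increases in BUN and creatinine" among common side effects. The GFR limit in 7.3 is an entry criterion only: "GFR (MDRD) of <15 at visit 0 (screening". Stopping for a renal event falls under the general clause in 13.1: "Adverse event that in the opinion of the investigator would be in the best interest of the subject to discontinue study treatment".

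**The concern.** A fixed level is crossed whether a value jumps or drifts. A ratio to the last value is crossed only by a jump, because each panel resets the reference. Closer panels split the same rise into smaller steps, so more frequent monitoring makes this alert less likely to fire. Panels are closest together at Visits 2, 3, 4 and 6 (weeks 5–11), around the escalation of spironolactone from 12.5 to 25 mg (9.1). The patients have diabetes and CKD and take an ACE inhibitor or ARB, and the section on potential benefits names renal failure as a risk to be weighed.

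At stake is a missed automatic prompt for a patient whose renal function has roughly halved. If GFR is about inverse to creatinine (an assumption), a patient who enters with GFR below 30 and whose creatinine doubles ends below 30/2 = 15, the value that would have barred entry.

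**Working it through.** **1. Is there another trigger?** Sections 10.1–10.3 give graded actions for potassium (>5.0, >5.5, >6.0) and none for creatinine. The dose-adjustment clause in 9.3.3 names potassium and blood pressure. Section 12.1 adopts CTCAE but reproduces only its general table, and it grades laboratory findings according to judgment. Section 13.1 rests on the investigator's opinion, and section 14 sets DSMB review every 3 months. None is an immediate creatinine notice.

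**2. What the rule lets through.** Over k equal steps, creatinine doubles when each step is 2^(1/k):
- k = 2: 1.41
- k = 4: 1.19
- k = 6: 1.12

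All are below 2, so nothing fires. Over two steps any cumulative rise below 2² = 4 can pass; for example 1.99² = 3.96. With illustrative values of 1.5, 2.2 and 3.0 mg/dL, the steps are 1.47 and 1.36 (no alert), while the ratio to screening is 2.0 (alert). The last-value rule is still needed: 1.5, 1.4, 2.9 gives 2.9/1.4 = 2.07 (alert) but 2.9/1.5 = 1.93 from screening (no alert).

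**3. How often each rule would fire.** The documents give no creatinine variability, so I assumed lognormal measurements with within-patient CV of 5, 10, 15 and 20%. I simulated 400,000 courses at weeks 1, 5, 6, 8, 11, 25 and 53 (Visits 0, 2, 3, 4, 6, 7, 8).

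*Rise over weeks 5–11, then stable and not yet noticed.* This is the case that can still occur. Percent alerted at CV 5/10/15/20%:

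| True rise | Visit 0 rule, at Visit 7 | Visit 0 rule, at Visit 7 or 8 |
|---|---|---|
| 2.0× | 50.0/50.2/49.9/50.0 | 66.8/66.6/66.6/66.7 |
| 2.25× | 95.2/79.8/71.1/66.1 | – |
| 2.5× | 99.9/94.3/85.6/78.8 | 100/98.6/94.5/90.5 |

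The last-value rule fires in 0/0/0.05/0.7% at Visit 7 and 0/0/0.1/1.3% at Visit 7 or 8.

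*Same rise, whole schedule.* By Visit 6 the Visit 0 rule fires in 50.1/50.0/50.5/52.0% (2.0×) and 99.9/94.3/85.8/79.7% (2.5×). The last-value rule ever fires in 0/0.8/6.9/19.2% and 0/5.0/17.1/31.8%.

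*Rise spread evenly over weeks 1–53.* The Visit 0 rule ever fires in 50–52% (2.0×) and 79–99.9% (2.5×), but by Visit 7 in only 0–12% and 0–20%. Most flags come at exit, so the gain is small.

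**4. Extra alerts.** With a sustained true ratio m to Visit 0, one comparison alerts with probability P(Z > (ln 2 − ln m)/(√2·s)), where s = √ln(1 + CV²). At most 50 patients × Visits 7 and 8 = 100 comparisons remain. Expected alerts:

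| | CV 10% | CV 15% | CV 20% |
|---|---|---|---|
| Stable (m = 1) | 100 × 4.5e-7 ≈ 0.00004 | 100 × 5.1e-4 ≈ 0.05 | 100 × 6.7e-3 ≈ 0.7 |
| All at m = 1.3 | 100 × 1.1e-3 ≈ 0.1 | 100 × 0.0206 ≈ 2 | 100 × 0.062 ≈ 6 |

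Over all 50 × 6 = 300 post-screening comparisons the figures are about 0.0001, 0.15 and 2.0 when stable, and 0.3, 6 and 19 at m = 1.3. At CV 5% all are near zero.

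**The case against.** The list is headed as urgent and sits beside chest pain and very low blood pressure. A jump since the last panel is a coherent trigger for an acute event, and slow drift can reasonably be left to other controls. There are several: change in creatinine is a named safety evaluation (3.2, 6.3), the study physician adjusts dose on safety labs (9.3.3), abnormal laboratory findings can be adverse events (12.1), the investigator reviews and verifies all data (16.1), and the DSMB meets every 3 months (14). The COVID-19 plan also ties the length of an extended prescription to recent bloodwork and medical judgment.

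These controls may well catch a rise, but all rest on someone judging the trend. None supplies the immediate notice that 11.3 exists to give.

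The simulation is also open to challenge. The modeled rises are smooth, which suits the present rule least. If the whole rise falls within one interval (a step at Visit 3), the last-value rule fires in 50–52% at 2.0× and 80–99.9% at 2.5×. That is correct, and the contrast above is conditional on a gradual rise, which is the only case this point covers. The 50% and 67% at 2.0× follow from the threshold lying at the true value and say little about this trial.

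The reach is small, and this objection stands. Section 11.3 states: "The new public health mandates concerning the COVID-19 have led to the decision to permanently close enrollment". Three sites had enrolled nobody, 50 is a ceiling, and the case that still matters needs an early doubling that went unnoticed while panels were closest together. The GFR limit of 15 is an entry criterion, so its use here only illustrates scale.

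**Conclusion.** The concern holds. As written, 11.3 gives no immediate notice of a creatinine doubling from screening when each step stays below twofold, and the document prints no other automatic renal trigger. This follows from the wording of the rule and needs only two panels after screening, so the damaged schedule table does not affect it.

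The size depends on assumptions: CV of 5–20%, a smooth rise, and a plateau not yet noticed. For an early 2.5× rise the alert rate at Visit 7 or 8 would go from 0–1.3% to 91–100%. The number of patients affected is unknown, because the document gives neither a doubling rate nor a count of active participants. The change is worth making because it is cheap and concerns safety. It does not show that any rise has gone unseen.

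**What to change.** In 11.3, extend the creatinine item so that it fires on a doubling from the last value *or from Visit 0 (screening)*. Keep the existing trigger.

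Name the reference where an older result qualified the patient, since 7.1 states: "Labs drawn within 3 months of the screening visit may be used to determine eligibility". That earlier value should serve as the reference for such patients, and its age may add noise.

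Add each patient's maximum creatinine ratio to Visit 0 to the 3-monthly DSMB safety tables, computed for everyone already enrolled from panels already collected. This covers the early visits that the alert can no longer reach.

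The cost is one phrase and one derived column, with no new tests or visits, plus the extra alerts estimated above. The change does not shorten the gap between Visits 7 and 8 (53 − 25 = 28 weeks on my reading of the schedule) or remedy lab delays under the COVID-19 plan.
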